Proportions of Patients and Eyes in the EAP with CRR from VA Nadir following 6 months and 12 months of treatment

CRR from Nadir	Patients		Eyes		Treatment duration at assessment [months]			
in the Efficacy Population	all	CRR	all	CRR	mean	(SD)	min	max
Patients with 6m assessment available	62	CRR at 6m 19 (30.6%)	124	CRR at 6m 30 (24.2%)	5.8	(1.0)	3.1	8.1
12m assessment available	47	CRR at 12m 17 (36.2%)	94	CRR at 12m 28 (29.8%)	11.6	(1.3)	9.1	13.9
at last observation	69	CRR at last obs. 34 (49.3%)	138	CRR at last obs. 55 (39.9%)	15.4	(9.0)	2.8	36.2

6m assessment : closest to 6 months, values at 3-9 months considered

12m assessment: closest to 12 months, values at 9-15months considered

Source Tables : EAP 01-01, EAP 01-02, EAP 01-03, EAP 02-01, EAP, 02-02, EAP 02-03

Magnitude of Recovery in Eyes in the EAP with CRR from VA Nadir at the 6 month, 12 month or at the last observation

Recovery* from Nadir [logMAR]**	N	mean	SD	median	max	min
at the 6 month vist	15	-0.47	0.31	-0.38	-1.00	-0.14
at the 12 month vist	15	-0.62	0.48	-0.40	-1.40	-0.10
at last observation (mean treat. dur. 20.9 m)	15	-0.93	0.42	-1.08	-1.44	-0.14

^{*}for eyes with CRR from BL where recovery had occured at the 6 months visit and a 12 month visit was available, too

Note, for these 15 eyes the VA at BL was also the VA at Nadir

Furthermore, data from the RHODOS and from the EAP provide evidence that the LHON-causative mutation harboured is prognostic of CRR in VA.

Therefore, secondary objectives of this study are to provide information on the effect of treatment duration on both the proportions of patients presenting with CRR and on the magnitude of any response with increasing treatment time and on the influence of the mutation harboured on CRR rate compared to spontaneous CRR (sCRR) untreated control patients.

The study will also allow the assessment of the safety and tolerability of long-term treatment with idebenone, with particular emphasis on the proportion of patients experiencing elevated Liver Function Tests (LFTs) or changes in blood cell counts.

^{**}off chart set to 1.70 [logMAR]

2 Study Objectives and Endpoints

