As SNT-CRS-002 study was completed (Clinical Study Report version 1.0 dated 15 July 2019), the data collected in the natural history studies has now been checked for the estimate of the responder rate. Based on the combined data from 175 eyes in the two natural history studies (SNT-IR-006 and SNT-CRS-002), the estimated responder rate is below 22%, i.e. lower than the initially expected rate of 24%. Although the determination of the exact responder rate for the natural history studies requires final data from the LEROS study for matching purposes, it is reasonable to assume that the responder rate of the natural history studies is not higher than 22%. The sample size for LEROS study is therefore re-calculated using the same methods as in the original protocol (Version1.0, 29 January 2016). In order to reach a power of 90% for the comparison of the responder rates between the natural history studies (assumed to be 22% instead of 24%) and the LEROS study (assumed to be 40%, as defined in the protocol), evaluable data from altogether 110 eyes from the LEROS study is required. In order to account for a drop-out rate of 30% (as defined in the protocol), at least 80 patients (equal to 160 eyes) will be enrolled to the LEROS study.

The sample size calculation was done with nQuery Advisor version 8.3.

For the sample size for the eye treated >1 year after the onset of symptoms and the corresponding external natural history control group, the aim is to collect VA data from same number of eyes as for the primary objective in order to compare the patients treated ≤1 and >1 year since the onset of symptoms and to compare patients treated with Raxone >1 year since the onset of symptoms with the corresponding natural history control group, assuming sufficient natural history control data can be collected to generate the natural history control group as described in 8.3.2.

Study: SNT-IV-005

V1.0 07 June 2021

7 Statistical hypotheses

The primary aim of the analysis is to show the superiority of Raxone® (patients treated ≤1 year after onset of symptoms) versus matching NH IDE naïve patients in proportion of eyes with clinically relevant recovery of VA from BL or 12 month maintenance of BL VA better than 1.0 logMAR

H₀: Raxone® (patients treated ≤1 year after onset of symptoms) is not superior to matching NH IDE naïve patients in proportion of eyes with CRR of VA from BL or 12 month maintenance of BL VA better than $1.0 \log MAR$

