In the statistical analyses a p-value less than 0.05 will be considered as statistically significant. If not stated otherwise, all tests will be performed as two sided tests and two sided 95% confidence intervals will be produced for the treatment differences.

CRS-1, CRS-2 and LEROS data will be presented in separate listings (one per study).

Unscheduled or repeat assessments in LEROS will not be included in summary tables, but will be included in listings.

Otherwise specified, listings will be sorted by patient number and visit date.

Deviations from the statistical plan will be reported in the clinical study report, including the rationale for the deviation.

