Analysis method: This outcome will be analysed by means of descriptive statistics and a complementary analysis using Kaplan-Meier method in the LEROS ITT population and in the subgroups specified in section 9.3. Survival analysis will use CRR as an event, months in treatment at CRR as time of event, and months at last assessment during treatment as censoring. It will be presented the cumulative percent curve of CRR using months since BL at CRR as variable. Inverse Kaplan-Meier curves of time (in months) to CRR (with number of eyes at risk and censored at 6, 12, 18 and 24 months) will be presented.

Table 12-3 - LEROS ITT eyes with CRR from Nadir at 24 months

	Variable		Analysis sets				
Eyes with CRR from Nadir	Variable Type ¹	LEROS ITT	mtDNA subgroups ⁴	Age at BL subgroups 4	Best VA BC at BL subgroups 4		
CRR	N	х	х	Х	х		

SNT-IV-005 Statistical Analysis Plan

Confidential

Months in treatment since BL at CRR ²	С	Х	Х	Х	х
Time in treatment at CRR by follow-up ^{2,3}	N	Х	Х	Х	х
Change in logMAR compared to BL at CRR ²	С	Х	Х	Х	х
Change in logMAR compared to BL at 24 months ²	С	Х	х	Х	х
CRR Kaplan-Meier analysis	-	Х	х	х	Х

Variable Type: nominal (N), ordinal (O), continuous (C); Only eyes with CRR from Nadir should be accounted; Time in treatment categories defined in section 16; Subgroups are to be analysed as defined in 9.3;

Outcome: Patients with CRR from Nadir (as defined in section 16) at 24 months (and related information, Table 12-2) considering time symptoms onset in the most recent affected eye at BL.

Analysis method: This outcome will be analysed by means of descriptive statistics and a complementary analysis using Kaplan-Meier method in the LEROS ITT population and in the subgroups specified in section 9.3. Survival analysis will use CRR as an event, months in treatment at CRR as time of event, and months at last assessment during treatment as censoring. It will be presented the cumulative percent curve of CRR using months since BL at CRR as variable. Inverse Kaplan-Meier curves of time (in months) to CRR (with number of patients at risk and censored at 6, 12, 18 and 24 months) will be presented.

Table 12-4 - LEROS ITT patients with CRR from Nadir at 24 months

Patients with CRR from	with CRR from Variable		Analysis sets				
Nadir	Type ¹	LEROS ITT	mtDNA subgroups ⁴	Age at BL subgroups ⁴	Best VA at BL subgroups ⁴		
CRR	N	Х	Х	Х	х		
Months in treatment at CRR ²	С	Х	Х	Х	Х		
Time in treatment at CRR by follow-up ^{2,3}	N	Х	Х	Х	Х		

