13.8 Other safety variables

No other safety data are to be analysed.

V1.0 07 June 2021

14 Deviations from the analyses planned in the current study protocol

There are currently no deviations from the CRS-1 CSP (version 1), CRS-2 CSP (version 1.0) and SNT-IV-005 CSP version 3.0 dated 06 March 2019 and SNT-IV-005 CSP addendum COVID-19 version1.0 dated 29 May 2020

15 Data analysis procedures

Statistical data analysis will be performed by 4Pharma Ltd according to current SAP.

Statistical analysis, tables and patient data listings will be performed with SAS® version 9.4 or higher for Windows (SAS Institute Inc., Cary, NC, USA).

16 Definitions

2nd eye onset

Most recent affected eye at Baseline.

Baseline (BL)

LEROS BL

NH BL

Best Visual Acuity

VA of the eye with best logMAR at the visit. However, if both eyes are off-chart, regardless of the VA, both eyes are considered as best eye.

Note: best eye at BL may not be the same as best eye at 6, 18 and 24 months or last assessment.

Clinical Relevant Benefit (CRB)

Defined as the composite of CRR and CRS, i.e, if the eye/patient has a CRR and/or a CRS then the eye/patient has also a CRB.

Clinical Relevant Recovery (CRR)

CRR is defined as improvement

or

- from "off-chart" (the equivalent of CF, HM, LP or NLP) VA to at least 1.6 logMAR value
 - of at least 0.2 logMAR value within "on-chart". Clinical Relevant Stabilization (CRS)

Is defined as maintenance of VA <1.0 logMAR in eyes with VA <1.0 logMAR at BL.

Clinical Relevant Worsening (CRW)

For any "on-chart" VA, CRW is defined as the disability to read at least 10 additional letters (equivalent to two chart lines) or a worsening to off-chart values (the equivalent of CF, HM, LP or NLP).

SNT-IV-005 Statistical Analysis Plan

Confidential

Delta onset

Is the time between symptoms onset of both eyes: date 2nd symptoms onset – date 1st symptoms onset. Patients will not be considered for calculating Delta onset if only one eye is affected or both eyes have the same date of symptom onset.

Months in Treatment

Months in treatment is only applied to LEROS patients. It is defined as time since BL to last follow-up during treatment period.

Nadir

Is the defined when VA reaches its worst point (highest logMAR or off-chart value). Time of nadir is the first time that nadir is reached.

Off-Chart

It is considered off-chart any VA entered as

- CF, HM, LP or NLP
- Any value above 1.68 logMAR

Patients ≤1 year after the onset of symptoms

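### SAP Tables 12-3 and 12-4 classify and time recovery from nadir but report its size against baseline, so an eye counted as recovered can be shown as having worsened

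*SAP*

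**What the plan says.** SAP section 12.3 defines four related outcomes: CRR from baseline and CRR from nadir, each for eyes and for patients (Tables 12-1 to 12-4). All are restricted to LEROS ITT and its subgroups, with no natural history comparator.

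In Table 12-3 the footnote to the timing and size rows reads "Only eyes with CRR from Nadir should be accounted", and Table 12-4 carries the same footnote. The two size rows of Table 12-3 are "Change in logMAR compared to BL at CRR" and the corresponding change at 24 months. Table 12-4 has change from baseline at the first CRR and best change from baseline at 24 months. These four rows match those in Tables 12-1 and 12-2.

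Section 16 places nadir where "VA reaches its worst point (highest logMAR or off-chart value"), dated to its first occurrence. CRR is a gain of at least 0.2 logMAR on-chart, or a move from off-chart to at least 1.6. Neither definition asks for a confirming reading. For the time-to-event part, "Survival analysis will use CRR as an event, months in treatment at CRR as time of event".

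Protocol section 1.2 tabulates the size of recovery in the Expanded Access Program (EAP) from nadir, and adds: "Note, for these 15 eyes the VA at BL was also the VA at Nadir".

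**The concern.** A table of recovery from nadir should say how large that recovery was. Here a reader learns which eyes recovered from their worst point and when, but the size is measured from another reference. In the EAP eyes this made no difference, because the two references coincided. In LEROS they need not. Patients may enter early in the disease, protocol section 1.1 says acuity falls to counting fingers in up to 80% of cases, and the SAP itself plans a time-to-nadir analysis from baseline (section 11.2.2) and tables of worsening from baseline (section 12.3).

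At stake is the reported magnitude of response in these tables. The study's secondary aims include the effect of treatment duration on acuity, and the protocol's rationale is that both the rate and the size of recovery grow with time on drug.

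A second, smaller matter is the rate. The reference is the worst recorded reading, later readings are compared with it, and there is no control arm. Regression from an unusually poor reading can therefore count as recovery.

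**Working it through.** **1. Rows side by side.** Each of Tables 12-3 and 12-4 has six rows.

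- CRR, the two timing rows and the Kaplan-Meier row follow CRR from nadir.
- The two change-in-logMAR rows use baseline.
- Table 11-3 gives the acuity level at nadir and months from baseline to nadir, but no change from nadir.
- Carry-over of wording is the likely cause. The nadir outcomes in section 12.3 cite Tables 12-1 and 12-2 as their related information, and the title of the nadir maintenance table (12-6) refers to maintenance of CRR from baseline.

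**2. Size.** For one eye, with acuity in logMAR (higher is worse):

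change from baseline = change from nadir + (nadir − baseline)

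If baseline can itself be the nadir, then nadir ≥ baseline, and the baseline row can never show more recovery than occurred from nadir. The two agree only when nadir equals baseline.

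| Baseline | Nadir | Later | Nadir − baseline | Change from nadir | Printed (from baseline) |
|---|---|---|---|---|---|
| 0.20 | 1.60 | 1.30 | 1.40 | −0.30 | −0.30 + 1.40 = +1.10 |
| 0.50 | 1.60 | 1.30 | 1.10 | −0.30 | −0.30 + 1.10 = +0.80 |

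Both eyes meet the 0.2 rule from nadir, and both would be printed as a worsening. This step needs no assumption about measurement error.

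**3. Rate.** The plan states no figure for recovery from nadir, so there is none to reproduce. The schedule in protocol section 6.1 gives baseline plus seven on-treatment visits (Months 1, 3, 6, 9, 12, 18 and 24), that is eight readings. SAP section 9 keeps unscheduled readings out of summary tables.

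The simulation used 300,000 on-chart eyes with no true change and eight independent normal readings, rounded to one letter (0.02 logMAR). Recovery was a gain of at least 0.2. The SD per reading is **assumed**.

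| False recovery, % of stable eyes | SD 0.03 | 0.05 | 0.07 | 0.10 | 0.15 |
|---|---|---|---|---|---|
| Any reading after the overall nadir | 0.0 | 7.2 | 33.5 | 63.2 | 78.5 |
| Month 24 reading only, against nadir | 0.0 | 2.1 | 12.4 | 32.1 | 52.5 |
| After nadir, at two consecutive visits | 0.0 | 0.6 | 6.9 | 25.6 | 48.1 |
| Any visit, against baseline | 0.0 | 2.1 | 12.6 | 31.9 | 52.7 |
| Month 24 only, against baseline | 0.0 | 0.4 | 2.8 | 9.0 | 18.5 |

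The last row can be checked by hand. With one-letter rounding, a recorded gain of at least 0.20 corresponds to a true difference of about 0.19 or more. The difference of two readings has SD √2 × 0.10 = 0.141, and P(Z ≥ 0.19/0.141) is about 9.0%.

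The false any-visit curve also climbs with follow-up. At SD 0.10 it reaches about 22%, 42%, 52% and 63% by Months 6, 12, 18 and 24.

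**The case against.** The strongest reply is that the tables do what their labels say. Rows headed as change from baseline will contain change from baseline. That is informative for such eyes, and the nadir level appears in Table 11-3. This stands to the extent that no number would be wrong for its label. It does not remove the gap: nothing in the plan reports the size of the recovery these tables count, although the protocol's own EAP table does.

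A reader might infer that Tables 12-3 and 12-4 measure recovery from baseline throughout. The documents do not support that: classification, timing and the Kaplan-Meier event all use nadir, and only the four size rows do not.

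A reader might also infer that noise certainly inflates the reported rate. Several points stand against this:

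- The documents give no reading SD, and at 0.03 the inflation is nil. Protocol section 7.1 requires refraction at every visit, specialist testing and letter-by-letter scoring, which should limit error.
- The simulation covers stable on-chart eyes only. From an off-chart nadir the rule is reaching 1.6, which is harder to meet by chance for eyes far off-chart.
- The CRR outcomes are headed as at 24 months, and the maintenance analyses use the same phrase. The count may therefore rest on the Month 24 reading alone, while the time-to-event rows use any visit. The SAP does not say.

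Finally, a reader might want two-visit confirmation as the main event rule. CRR rests on a single assessment throughout the trial, visits after Month 12 are six months apart, and Visit 9 is off treatment. Confirmation would drop late responders and still leave about 26% false recovery at SD 0.10. It fits only as a sensitivity analysis.

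**Conclusion.** The point holds for the size rows. All four change-in-logMAR rows in Tables 12-3 and 12-4 use baseline, and no row gives change from nadir. The shortfall for each eye is exactly nadir minus baseline, and it can turn a counted recovery of 0.30 into a printed worsening of 1.10. The direction rests on one assumption, that baseline is eligible as the nadir; the SAP does not state this. How many LEROS eyes are affected cannot be known from the documents.

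On the rate, the documents support only a possibility. For stable on-chart eyes under an any-visit rule, false recovery runs from nil at an assumed SD of 0.03 to about 7% at 0.05 and 63% at 0.10. If only Month 24 counts, the figures are 0%, 2% and 32%.

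These are additional, descriptive, LEROS-only outcomes. The primary endpoint, its model and the 110-eye sample size are untouched.

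**What to change.** - In Tables 12-3 and 12-4, report change in logMAR from nadir at CRR (first CRR for patients) and at 24 months. Keep change from baseline as an extra, clearly labelled row.
- State whether CRR at 24 months means the Month 24 reading or any visit up to it, and use that meaning in the tables and the maintenance analyses.
- State that CRR must occur after the nadir, and which visits can supply the nadir (whether baseline counts, and whether Visit 9 does).
- Point the nadir outcomes to Tables 12-3 and 12-4.
- As a sensitivity analysis only, add a Kaplan-Meier curve in which CRR counts if present at two consecutive scheduled on-treatment visits, dated to the first. Keep the planned curve as the main one.

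The cost is SAP wording and a little programming; no new data are needed. The drawback of the confirmed curve is that it misses late responders, including any eye whose first CRR is at Month 24, and this should be stated beside it.

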12.4 Sensitivity analysis due COVID-19 pandemic

Due to the COVID-19 pandemic, study visits can be rescheduled within

- Visits 6 and 7 it is 90 days,
- Visit 9 it is 60 days.
- Visit 8 if

SNT-IV-005 Statistical Analysis Plan

Confidential

Study: SNT-IV-005

- ≤ 60 days later than planned visit per protocol and ≤30 days no study medication intake at rescheduled visit 8 then visit 8 was performed
- >60 days later than planned visit per protocol and >30 days no study medication intake at rescheduled visit 8 then visit 9 was performed and visit 8 was skipped

of originally scheduled visit date.

The impact of the rescheduling or visits missed due to COVID-19 will be investigated with a sensitivity analysis using the approach proposed by Meyer et al (2020).

At the time of 12 months follow-up (Visit 6) only one patient missed the visit due to COVID-19 pandemic. Therefore, sensitivity analysis will be used in mITT population on the 24 months data (Visit 8).

Post-treatment data (Visit 9) will not be imputed.

All missing data will be categorized as being missing due to COVID-19 or due to other causes. In the first step, the missing data due to COVID-19 will be imputed using the assumption of MAR. In the second step, the remaining missing data will be imputed using the assumption of MNAR. For observations MNAR, last-observation-carried-forward will be applied, using only data collected from month 12 visit (Visit 6) onwards. For patients with no data in this time frame, the data from the follow-up visit will be used as the 24 month assessment. This sensitivity analysis will be repeated for a dataset where the Visual Acuity assessments that were delayed by more than 30 days from the scheduled visit date will be set as missing and included in the category of missed assessments due to COVID-19.

For the missing data assuming MAR, the multiple imputation approach will be applied. The imputation will consider and use only LEROS data, since the matched external natural history control group is not longitudinal data and does not include any missing data. As the disease does not progress linearly, only the 12 month (Visit 6) and 18 month (Visit 7) data will be used for the imputations. First the MCMC methodology will be used to impute the data to obtain monotonously missing data. Then imputation will be completed using regression imputation for the monotonously missing data. Analysis model will be run for the imputed data by imputation and SAS procedure *mianalyze* will be used to calculate the combined results.

SAS code to perform multiple imputation on missing visual acuity results assuming MAR:

/* STEP 1: LEROS data imputation*/

/*impute non-monotonously missing observations */

proc mi data=visual acuity out=visual acuite monotone nimpute=1000 seed=xxx;

var logMAR_v6 logMAR_v7 logMAR_v8;

```
mcmc chain=multiple impute=monotone;
run;
/*use regression imputation to complete MAR imputation*/
proc mi data= visual_acuite_monotone out=visual_acuite_impute=1 seed=xxx;
  var logMAR_v6 logMAR_v7 logMAR_v8;
  monotone regression;
run;
    STEP 2: calculation of visit 8 CRB from baseline for imputed values
             visit 8 CRB from baseline should be calculated with the same SAS code
             used for the main analysis of the primary endpoint but use visit 8 as main variable
             input dataset: visual acuite imputed;
             calculate LEROS visit 8 CRB;
             output dataset: leros crb imputed
*/
    STEP 3: repeat 1000 times Natural History data used the main analysis of the
             primary endpoint and join with LEROS data set which has the imputed CRB calculation*/
data natural history repeated;
  set natural history analysis data;
    do Imputation = 1 to 1000;
       output;
    end;
  run;
data all data joined;
        set leros crb imputed natural history repeated;
run;
    STEP 4: applying logistic model over the new imputed CRB data*/
proc sort data= all_data joined; by Imputation; run;
proc logistic;
   by _Imputation_;
```

```
class treatment gender mutation / param=ref;
   model CRB(event='1') = treatment gender mutation / link=logit clodds=pl;
   ods output ParameterEstimates = ParameterEstimates;
   ods output CLOddsPL = CLOddsPL;
run;
     STEP 5: calculate the logistic analysis combined results*/
proc mianalyze parms(classvar=classval)= ParameterEstimates.;
   modeleffects treatment gender mutation;
run;
     STEP 6: calculate the combined results odds ratio */
/* Transform estimates */
data calculated_odds_ratio_1;
   label or_value = 'Log odds ratio value'
        or stderr = 'Log odds ratio SE';
   set CLOddsPL;
     or_value = log(OddsRatioEst);
     or stderr=(log(uppercl)-log(lowercl))/(2*1.96);
run;
/* Combine transformed estimates */
proc sort data= calculated_odds_ratio_1; by Effect; run;
proc mianalyze data= calculated_odds_ratio_1;
       by Effect;
       modeleffects or_value;
       stderr or stderr;
       ods output ParameterEstimates = calculated_odds_ratio_2;
     run;
```

```
/* Back-transform combined values */
data;

label estimate_back = 'Odds ratio'

lcl_back = 'LCL Odds ratio';

set calculated_odds_ratio_2;

estimate_back = exp(estimate); *pooled odds ratio;

lcl_back=estimate_back*exp(-1.96*stderr); *pooled lower limit;

ucl_back=estimate_back*exp(+1.96*stderr); *pooled upper limit;

run;
```

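### The program printed in SAP 12.4 has no place for the MNAR half of the Month 24 COVID-19 sensitivity analysis, so as printed it gives what is in effect an all-MAR result

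*SAP*

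**What the plan says.** The text of SAP 12.4 sets out a method that depends on cause:

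- Classification: "All missing data will be categorized as being missing due to COVID-19 or due to other causes".
- COVID-19 gaps: "In the first step, the missing data due to COVID-19 will be imputed using the assumption of MAR".
- Other gaps: "In the second step, the remaining missing data will be imputed using the assumption of MNAR".
- How the MNAR step works: "For observations MNAR, last-observation-carried-forward will be applied, using only data collected from month 12 visit (Visit 6) onwards". The fallback is: "For patients with no data in this time frame, the data from the follow-up visit will be used as the 24 month assessment".
- Scope of multiple imputation: "For the missing data assuming MAR, the multiple imputation approach will be applied".

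The analysis is in the mITT population at Month 24 (Visit 8). It is to be repeated with assessments delayed by more than 30 days set to missing and counted as COVID-19 gaps.

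A six-step SAS program follows. STEP 1 has two PROC MI calls, each with the list "var logMAR_v6 logMAR_v7 logMAR_v8". The second call is annotated "use regression imputation to complete MAR imputation". STEP 2 takes the imputed dataset as input and derives Visit 8 CRB (clinically relevant benefit). STEPS 3 to 6 append the natural history data, fit the logistic model and pool the odds ratio.

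**The concern.** The text and the program describe two different analyses. The text separates gaps by cause and gives non-COVID gaps a different treatment. The program contains no cause variable, no carry-forward and no use of the follow-up visit, and it runs without a break from imputation to the pooled odds ratio. A programmer who follows it gets no opportunity to apply the second step.

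This matters because the second step of SAP 12.4 is the only handling of missing data in either document that is labelled MNAR. The imputation for the Month 12 primary endpoint in SAP 12.1.1 is explicitly MAR, and the default in SAP 9.1 is to leave missing data out. If the printed program is followed, the one analysis meant to vary the assumption for non-COVID drop-out does not vary it, yet its label says that it does. A reader of the study report could not tell.

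**Working it through.** SAP 12.4 states no sample size, power or rate for this analysis, so there is no figure to reproduce. The check is a comparison of text and program.

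| Element | Text of SAP 12.4 | Printed program |
|---|---|---|
| Cause of each gap | Classified as COVID-19 or other | No flag, no WHERE or BY restriction |
| COVID-19 gaps | Multiple imputation, MAR | Multiple imputation, MAR |
| Non-COVID gaps, some Visit 6 to 8 value present | LOCF from Visit 6 onwards | Multiple imputation, MAR |
| Non-COVID gaps, nothing from Visit 6 on | Follow-up visit value | Rule never applied |
| Input to Visit 8 CRB | Data after both steps | Output of PROC MI |

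**Tracing the calls.** The first PROC MI call uses MCMC to fill intermittent gaps until each eye has a monotone pattern. What then remains is the run of missing values after an eye's last observed visit, which is the typical drop-out pattern that the MNAR step is meant to handle. The second call fills that run by regression on the earlier visits. For any eye with at least one Visit 6 to 8 value, no gap is left. STEP 2 reads that dataset directly.

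**Illustration.** I emulated the two calls on simulated eyes: a conditional-normal fill of intermittent gaps, then sequential Bayesian regression over Visits 6, 7 and 8. The 160 eyes and the 30% with missing data borrow the planning figures in SAP section 6. Everything else is assumed: 10%, 30% or 50% of affected eyes have a COVID-19 gap (one missing value, at Visit 7 or 8), and the others drop out from Visit 6, 7 or 8 onwards. There is one simulated dataset per scenario.

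| COVID-19 share | Missing values | COVID-19 / other | Left after both calls | Other gaps at Visit 8 | Eyes with Visits 6 to 8 all missing | Other Visit 8 gaps in eyes with some value |
|---|---|---|---|---|---|---|
| 10% | 90 | 3 / 87 | 0 | 51 | 12 | 51 − 12 = 39 |
| 30% | 93 | 15 / 78 | 0 | 35 | 13 | 35 − 13 = 22 |
| 50% | 69 | 24 / 45 | 0 | 24 | 6 | 24 − 6 = 18 |

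The last column counts the eyes for which the text requires LOCF at Visit 8 and the program gives a MAR draw. Eyes with all three visits missing are taken out because the emulation filled them from the marginal distribution, and I have not verified what SAS does with such rows. Whatever it does, the program never reaches for their follow-up visit value.

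**CRB in the same runs.** Mean Month 24 CRB, program against text, was 59.0% against 56.7%, 57.3% against 54.9% and 53.7% against 53.3%: differences of 2.3, 2.4 and 0.4 percentage points. These are not estimates for LEROS. They follow from assumed means, SD, correlations and drop-out patterns. The assumed mean acuity improves from Month 12 to Month 24 (logMAR 1.30 to 1.20), which by itself tends to make carried-forward values look worse. The text-rule figures also omit the eyes that need a follow-up visit value. The runs show only that the two routes differ.

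**The case against.** The best defence is that the program is only the MAR component. Its heading says it performs imputation assuming MAR, and the text confines multiple imputation to data so classed. It is visibly a template: the seed is a placeholder, the input dataset is undefined, and STEP 2 is a comment. Nothing says that it overrides the text, and the section defers to a published approach that is not reproduced.

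Much of this stands. A reader might infer that the sponsor intends to impute every gap under MAR, or that the executed program did so. The documents support neither; they show a mismatch between text and code.

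The defence does not remove the mismatch, because the printed program ends at the pooled odds ratio. The unwritten ways round it are these:

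- LOCF before PROC MI reverses the stated order and feeds carried-forward values into the imputation model as if observed.
- Removing eyes with non-COVID gaps beforehand drops eyes that the text says will be imputed. It also fails for an eye with a COVID-19 gap at one visit and another cause at the next; how often that occurs is not stated.
- Resetting non-COVID values after PROC MI works, but it is not there.

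A reader might also put a size on the problem by taking 30% of 160 = 48 eyes as wrongly imputed. The documents do not support that. The 30% is the drop-out allowance for evaluable primary-endpoint data, which are assessed at Month 12. Eyes lost before then would have no Visit 6 to 8 value and would fall under the follow-up visit rule, not LOCF. The share due to COVID-19 at Month 24 is not given.

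**Conclusion.** The point holds as a mismatch between the method described and the program printed. Followed as printed, the program fills non-COVID gaps under MAR in eyes with at least one Visit 6 to 8 value, and it applies neither the LOCF rule nor the follow-up visit rule. The Month 24 sensitivity analysis and its repeat with delayed visits set to missing would carry a COVID-MAR/other-MNAR label but would in effect be all-MAR.

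Three limits apply:

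- The treatment of eyes with Visits 6 to 8 all missing was not verified, so the claim that every missing value is filled should not be made.
- Neither the size nor the direction of the effect on the odds ratio can be obtained from the documents. A reader might infer that the Month 24 result would look falsely robust; that needs response rates the documents do not contain.
- The Month 12 primary analysis, its own sensitivity analyses and the sample size are not affected.

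Severity is moderate: a sensitivity analysis at a secondary time point, whose intended method is already written down.

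**What to change.** Amend the program in SAP 12.4 so that it follows the text:

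1. Carry a COVID-19/other flag for each eye and visit, using the classification already required.
2. After the two PROC MI calls, within each of the 1000 imputed datasets, keep the MAR draws only for values flagged COVID-19 and set those flagged as other back to missing.
3. Fill these by the written rule: LOCF from data collected at Visit 6 onwards, otherwise the follow-up visit value.
4. Only then derive Visit 8 CRB in STEP 2. STEPS 3 to 6 can stay as they are.
5. State whether an imputed COVID-19 value may be carried forward, for example from Visit 7 to Visit 8. The restriction to collected data suggests observed values only, but the SAP should say so.
6. State how eyes with no Visit 6 to 8 value pass through PROC MI.
7. Use the same order in the repeat run with visits delayed by more than 30 days set to missing.

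The cost is a few lines of code and two clarifying sentences, with no new data and no change to the stated method. If the analysis has already been run, check the executed program against the text and report any departure in the clinical study report, as SAP section 9 requires for deviations from the plan.
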